3.1.2. HYPOTHESIS TESTING

Non-inferiority (NI) hypothesis testing framework will be used in the primary analysis.

 $H_0: P_{Exper} - P_{Ctrl} \ge \delta$ $H_a: P_{Exper} - P_{Ctrl} < \delta$

Where δ is the NI margin and is defined to be 0.0015.

The hypotheses will be tested using comparison of the upper limit of the one-sided 97.5% Confidence Interval (CI) for the rate difference ($P_{Exper} - P_{Ctrl}$) to the non-inferiority (NI) margin δ . H_0 will be rejected and NI will be demonstrated if the above mentioned upper limit is less than the NI margin δ . Some hypothetical examples are presented in the Figure 1 below.

3.2. SECONDARY AND SENSITIVITY ANALYSIS

Secondary Analysis will be conducted using ITT population. Analysis involving plasma volumes will be conducted using MITT and PP populations.

Analysis of Severe Adverse Events. Given the historical rate of severe hypotensive (vasovagal/hypovolemia) adverse events according to the plasma center adverse event reporting system, based on the IQPP definitions, per donation in donors undergoing plasmapheresis is 1/10000, with probability more than 88% there will be not more than 2 severe hypotensive (vasovagal/hypovolemia) adverse events in 12000 plasmapheresis procedures. Given this historic rate expected number of severe hypotensive (vasovagal/hypovolemia) adverse events (vasovagal/hypovolemia) adverse events in 12000 plasmapheresis procedures. Given this historic rate expected number of severe hypotensive (vasovagal/hypovolemia) adverse events will be 1.2

ClinStatDevice

Statistical Analysis Plan Version: 1.0 Date: 26-Apr-2020

in each study arm. Thus, formal hypothesis testing will be conducted if there are more than 2 severe hypotensive (vasovagal/hypovolemia) adverse events in any of the two study arms.

Estimates of significant hypotensive (vasovagal/hypovolemia) AE incidence rates will be provided separately for experimental and control groups along with their 95% CIs based on the modeling framework outlined in the primary analysis section.

Secondary analysis will also include the estimation of significant hypotensive (vasovagal/hypovolemia) AE by total collected plasma volume. Modeling framework outlined in the primary analysis section with an additional covariate representing total volume of the collected plasma will be used. Similar statistical modeling framework will be used to estimate the incidence rates of significant hypotensive (vasovagal/hypovolemia) AE by collection time, and the number of collection cycles.

Survival analysis will be used to analyze the time-to-AE (significant hypotensive (vasovagal/hypovolemia)) data. Time to event is defined as time between the procedure start and the occurrence of the AE. Kaplan-Meier curves will be presented. Non-parametric Log-Rank tests will be conducted to evaluate differences between the two study groups. Survival modeling and hazard estimation will be used to obtain parameter estimates for the variables of interest. Other secondary objectives will be assessed with the use of continuous and discrete modeling techniques whenever applicable. Assessment and comparison of the relative rates will be conducted using repeat measure models and descriptive statistical techniques.

Statistical Analysis Plan Version: 1.0 Date: 26-Apr-2020

Effectiveness analysis will be conducted by comparing the distribution of collected plasma volumes across the two groups of the clinical trial.

Descriptive statistical summaries and advanced data visualization techniques will be used for data presentation.

Detailed description of the analysis related to the other secondary endpoints will be included in later versions of the SAP.

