# 5.2 Secondary Endpoints

- Incidence rate of severe hypotensive (vasovagal/hypovolemia) adverse events according to the plasma center adverse event reporting system, based on the IQPP definitions, per donation in donors undergoing plasmapheresis
- Incidence rate of significant hypotensive (vasovagal/hypovolemia) adverse events according to the plasma center adverse event reporting system, based on the IQPP definitions, relative to the actual plasma volume collected
- Time from start of plasmapheresis "Begin Draw" to the first significant hypotensive (vasovagal/hypovolemia) adverse event according to the plasma center adverse event reporting system, based on the IQPP definitions
- Incidence rate of significant hypotensive (vasovagal/hypovolemia) adverse events according
  to the plasma center adverse event reporting system, based on the IQPP definitions, in the
  subgroups of donors with a body mass of less than or equal to 130 lbs and those greater than
  130 lbs
- Incidence rate of significant hypotensive (vasovagal/hypovolemia) adverse events according to the plasma center adverse event reporting system, based on the IQPP definitions, in the subgroups of donors with a body mass index (BMI) of less than or equal to 30 and of those greater than 30
- Incidence rate of significant hypotensive (vasovagal/hypovolemia) adverse events according
  to the plasma center adverse event reporting system, based on the IQPP definitions, in the
  subgroups of donors defined by their respective status as a first-time donor or repeat donor
- Incidence rate of significant hypotensive (vasovagal/hypovolemia) adverse events according
  to the plasma center adverse event reporting system, based on the IQPP definitions, in the
  subgroups of donors defined by their gender
- Total plasma volume collected per procedure

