### 9.5 Secondary Analysis

Analysis of the secondary endpoints will be outlined in the SAP. Continuous and discrete modeling techniques will be used whenever applicable.

Effectiveness analysis will be conducted by comparing the distribution of collected plasma volumes across the two groups of the clinical trial.

The rates of AEs will be assessed relative to plasma volume, collection time, and the number of collection cycles. Assessment and comparison of the relative rates will be conducted using repeat measure models and descriptive statistical techniques. The secondary analysis – assessing time to adverse events – will be conducted using a survival analysis modeling framework and hazard estimation. Subgroup analysis will be based on descriptive statistical summaries. Descriptive statistical summaries and advanced data visualization techniques will be used for data presentation.

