2.2.2. STUDY POPULATIONS

The ITT data set will consist of all study donations were the apheresis procedure was started by "Begin Draw" on the NexSys® PCS device. The ITT population will include all Study Adverse Events.

The Modified Intent to Treat (MITT) data set is a subset of the ITT data set which consists of all complete study donations, as well as all donations associated with a moderate or severe adverse event [not just hypotensive (vasovagal/hypovolemia)] defined according to the IQPP and associated with the study donations. A donation is considered complete if the total plasma volume collected is at least 200 mL. A donation is considered incomplete if the total plasma volume collected is less than 200 mL.

The Per-Protocol (PP) data set will consist of all donations without major protocol deviations where the apheresis procedure is successfully completed collecting at least 90% of the target plasma volume, as well as all study donations associated with a moderate or severe adverse event [not just hypotensive (vasovagal/hypovolemia)] defined according to the IQPP.

Statistical Analysis Plan Version: 1.0 Date: 26-Apr-2020

The Extended AE Population (EAEP) is defined as consisting of ITT population with the addition of all the AEs that were reported as associated with Non-Study donations in donors previously enrolled in the study and reported within two calendar weeks post study last day.

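### Total plasma volume per procedure is assigned to two analysis sets that are themselves selected on collected volume, with no explicit analysis of all started procedures; the per-protocol set is the main problem

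*SAP*

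**What the plan says.** The endpoint in Protocol 5.2 is "Total plasma volume collected per procedure", that is, per procedure and not per completed donation. Protocol 9.5 makes it the effectiveness measure: "Effectiveness analysis will be conducted by comparing the distribution of collected plasma volumes across the two groups of the clinical trial". SAP 3.2 repeats that plan, and neither place names an analysis set in that sentence.

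The sets are named at the start of SAP 3.2. The general rule is "Secondary Analysis will be conducted using ITT population". The next sentence covers volume: "Analysis involving plasma volumes will be conducted using MITT and PP populations".

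SAP 2.2.2 defines the sets as follows.

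- **ITT:** "The ITT data set will consist of all study donations were the apheresis procedure was started by" the Begin Draw step, whatever volume is reached.
- **MITT:** "complete study donations, as well as all donations associated with a moderate or severe adverse event" of any type. The threshold is "A donation is considered complete if the total plasma volume collected is at least 200 mL".
- **PP:** donations without major deviations "where the apheresis procedure is successfully completed collecting at least 90% of the target plasma volume", again plus all donations with a moderate or severe adverse event.

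The only other volume summary, in SAP 3.5, is limited to donations with significant or severe adverse events. Protocol 9.1 gives MITT and PP a sensitivity role only.

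**The concern.** Membership of MITT and PP depends on the quantity being compared, and it is decided after randomisation. The comparison is then of yield given that a procedure got far enough, while the endpoint and the benefit argument (Protocol 2.1 and 10.1: more plasma on average, possibly fewer procedures) concern yield per procedure started. A procedure stopped early still uses a donor visit.

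The two cuts act differently. The MITT cut is the same absolute volume in both arms. The PP cut is a fraction of the target, and the target is what the two nomograms set differently. Protocol 1.2 says a PPN procedure can take longer, so late stops could be more frequent in that arm. PP removes late stops below 90% of target unless a moderate or severe adverse event occurred.

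At stake is the size of the stated yield gain. The trial's safety conclusion does not depend on it.

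**Working it through.** **Inputs from the documents.** Expected mean volume is 777 mL (current nomogram) and 848 mL (PPN), a gain of 71 mL or 9.1% (Protocol 2.1). Control targets are 625, 750 and 800 mL by weight band (Protocol Table 1). The PPN cap is 1,000 mL. Donor weight is truncated normal, 110-400 lbs, with mean 211.2 and SD 50.85 (SAP Appendix 2). The share of procedures dropped from each set is not given, so every rate below is an assumption.

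**1. The plan's own figure.** The weight distribution puts 9.3%, 12.7% and 78.0% of donors in the three bands. The mean target is 0.0933 × 625 + 0.1268 × 750 + 0.7799 × 800 = 777.3 mL, against 777 stated. The stated figure therefore agrees with the mean programmed target, with no allowance for short collections. The 848 mL cannot be rebuilt, because the plasma-volume formula and the hematocrit distribution are not given. It is taken as stated.

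**2. How the PP cut works.** A donor with an 800 mL control target stays in PP from 0.9 × 800 = 720 mL. If the PPN target is 1,000 mL, the cut is 900 mL. A collection of 720-899 mL is then kept in control and dropped in PPN. For donors whose target falls under PPN (about 23.5%), the asymmetry runs the other way.

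Taking 777 and 848 mL as mean targets and setting the adverse-event exception aside, the PP floors average 0.9 × 777 = 699.3 mL and 0.9 × 848 = 763.2 mL. They are already 63.9 mL apart. If every retained procedure in both arms stopped exactly at its floor, PP would still show 63.9 of the 71 mL.

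**3. Gain over all started procedures.** Let f be the share dropped, v the mean volume of dropped procedures, and 777 and 848 the means of those kept (C = control, E = PPN):

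gain = [(1 − fE) × 848 + fE × vE] − [(1 − fC) × 777 + fC × vC]

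*MITT, v between 0 and 199 mL, the same in both arms:*

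| Control loss | PPN loss | Gain, all started (mL) | Overstatement in MITT (mL) |
|---|---|---|---|
| 1% | 1% | 70.3 | 0.7 |
| 2% | 2% | 69.6 | 1.4 |
| 5% | 5% | 67.4 | 3.6 |
| 2% | 3% | 61.1 to 63.1 | 8 to 10 |
| 2% | 4% | 52.6 to 56.6 | 14 to 18 |
| 3% | 2% (v = 100) | 76.4 | −5.4 (understated) |

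With equal loss f the overstatement is 71 × f, and the relative gain stays at about 9.1%. Each extra percentage point lost in PPN adds (848 − v)/100, or about 6.5 to 8.5 mL. With control loss of 0-5%, erasing the gain would need an excess in PPN of about 8 to 11 percentage points.

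*PP, dropped procedures averaging 30% to 85% of target:*

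| Control loss | PPN loss | Gain, all started (mL) | Overstatement in PP (mL) |
|---|---|---|---|
| 5% | 5% | 68.5 to 70.5 | 0.5 to 2.5 |
| 5% | 7% | 56.6 to 67.9 | 3 to 14 |
| 5% | 10% | 38.8 to 64.1 | 7 to 32 |

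**4. Which stops fall below 200 mL.** At 777 mL over an average of 4.3 cycles (Protocol 2.5), one cycle yields about 777 / 4.3 = 181 mL. The 200 mL line is therefore crossed around the first or second cycle.

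**The case against.** A reader might infer that failed procedures simply do not count, and that the yield gain is therefore overstated. The documents do not support that. MITT keeps every partial collection of 200 mL or more at its actual volume, and both sets keep any collection with a moderate or severe adverse event. Extra PPN time comes from added cycles towards a higher target, while pump speed and anticoagulant ratio are unchanged (Protocol 2.5). Stops caused by length would therefore mostly come after 200 mL and stay in MITT. Nothing in the documents shows that PPN has more very early stops, so the unequal-loss rows for MITT are illustrations only.

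Four further replies deserve weight.

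- *The ITT sentence already covers volume, which is a secondary endpoint.* This is possible, but the next sentence specifically names other sets for volume. If ITT is meant as well, the SAP should say so.
- *The nomogram target is the intervention, so any set reflects it.* This is true, but ITT and MITT also show how often the target is missed, whereas PP largely conditions that away.
- *MITT is planned beside PP, so a gap between them would expose late losses.* This is partly right. It does not say which set supports the claim, and it leaves collections under 200 mL without a moderate or severe adverse event out of both.
- *The comparison has no hypothesis, margin or success criterion.* This is correct, and it limits the consequence.

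**Conclusion.** The point holds in a limited form. As written, the SAP gives total volume per procedure no explicit analysis on all started procedures and ties it to two sets selected on the outcome.

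PP is the weaker basis. Its cut differs by arm for the same donor, and its mean is largely fixed by the targets. MITT is much less exposed: about 1 to 4 mL out of 71 if 1-5% of procedures are lost equally, more only if PPN has an excess of early stops, and in the opposite direction if control has the excess.

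Neither the direction nor the size of any bias can be established from the documents, because they give no rates of short collection. The figures also assume that 777 and 848 mL are the means of retained procedures. The primary safety analysis uses ITT and is not affected. The change is worth making because it is cheap and removes the selection.

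**What to change.** In SAP 3.2, state that the main comparison of total plasma volume per procedure uses ITT: every donation started by Begin Draw, with the actual volume collected, including values under 200 mL, and allowing for repeat donations by the same donor. Keep MITT and PP as supportive analyses only. Report by arm, beside the volume comparison, the share of procedures under 200 mL and the share under 90% of target.

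In the same edit, reconcile the set definitions. Protocol 9.1 retains short donations only for significant hypotensive events, while SAP 2.2.2 retains them for any moderate or severe adverse event and also excludes major deviations from PP.

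The cost is a sentence or two in the SAP and one extra table. Sorting donations into MITT and PP already requires a volume for each started donation. Protocol 13.1.1 does not say outright that volumes of aborted procedures are stored, so this should be confirmed with data management. The downside is that the stated yield gain may be slightly smaller.

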1.1.2. SECONDARY OBJECTIVES

- To assess if the incidence rate of severe hypotensive (vasovagal/hypovolemia) adverse events according to the plasma center adverse event reporting system, based on the IQPP definitions, per donation in donors undergoing plasmapheresis in the experimental group is NOT inferior to that seen in donors in the control group
- To assess the incidence rate of significant hypotensive (vasovagal/hypovolemia) adverse events according to the plasma center adverse event reporting system, based on the IQPP definitions, relative to the actual plasma volume of plasma collected, comparing procedures in the experimental group and control group
- To study the time from the start of plasmapheresis "Begin Draw" to the first significant hypotensive (vasovagal/hypovolemia) adverse events according to the plasma center adverse event reporting system, based on the IQPP definitions, in the experimental group and the control group
- To assess the incidence rate of significant hypotensive (vasovagal/hypovolemia) adverse events according to the plasma center adverse event reporting system, based on the IQPP definitions, of procedures in the experimental group and in the control group in the subgroups of donors with a bodyweight of less than or equal to 130 lbs and those greater than 130 lbs
- To assess the incidence rate of significant hypotensive (vasovagal/hypovolemia) adverse events according to the plasma center adverse event reporting system, based on the IQPP definitions, of procedures in the experimental group and in the control group in the

Statistical Analysis Plan Version: 1.0 Date: 26-Apr-2020

subgroups of donors with a body mass index (BMI) of less than or equal to 30 and of those greater than 30

- To assess the incidence rate of significant hypotensive (vasovagal/hypovolemia) adverse events according to the plasma center adverse event reporting system, based on the IQPP definitions, of procedures in the experimental group and in the control group in the subgroups of donors defined by their respective status as a first-time donor or repeat donor
- To assess the incidence rate of significant hypotensive (vasovagal/hypovolemia) adverse events according to the plasma center adverse event reporting system, based on the IQPP definitions, of procedures in the experimental group and in the control group in the subgroups of donors defined by their gender

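### The event-by-volume model in SAP 3.2 adjusts for collected volume, which an event can itself reduce; its coefficients can be biased, most in PP, and it does not by itself give the planned rate per volume

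*SAP*

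**What the plan says.** The secondary objective (SAP 1.1.2) is the incidence of significant hypotensive events "relative to the actual plasma volume of plasma collected, comparing procedures in the experimental group and control group". Protocol 9.5 plans the same for three measures: "The rates of AEs will be assessed relative to plasma volume, collection time, and the number of collection cycles". The statistical paragraph of the Protocol synopsis also speaks of rates per volume or per number of cycles.

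SAP 3.2 carries this out by extending the primary GEE logistic model: "Modeling framework outlined in the primary analysis section with an additional covariate representing total volume of the collected plasma will be used". A similar model is planned for the incidence of significant hypotensive "AE by collection time, and the number of collection cycles".

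On the analysis set, SAP 3.2 has two consecutive sentences: "Secondary Analysis will be conducted using ITT population" and "Analysis involving plasma volumes will be conducted using MITT and PP populations". SAP 2.2.2 defines those sets. MITT takes complete donations, where "A donation is considered incomplete if the total plasma volume collected is less than 200 mL". PP requires at least 90% of target and no major protocol deviation. Each set then adds back donations with a qualifying event; for PP the wording is "as well as all study donations associated with a moderate or severe adverse event", of any type. Protocol 9.1 adds back only donations with a significant hypotensive event, so it has the same asymmetry.

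**The concern.** Collected volume, collection time and number of cycles are known only when the draw ends. If a hypotensive event ends the draw early, all three are lowered by the outcome that they are meant to explain.

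The MITT and PP rules add selection. An event-free draw below 200 mL (MITT) or below 90% of target (PP) leaves the set; a draw of the same size with an endpoint event stays. In PP, apart from donations kept for another moderate or severe event, a short draw is in the data only because it had an endpoint event.

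At stake is the trial's own question, whether collecting more plasma is safe. A volume effect that is nil, or even harmful, could be reported as protective. Because the arm sets the target volume, the arm coefficient in the same model can move as well. A volume-adjusted odds ratio is also not a rate per litre, so the planned comparison between arms is not delivered by this model alone.

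**Working it through.** **Inputs from the documents.** Weight: truncated normal, mean 211.2, SD 50.85, range 110–400 lbs (SAP Appendix 2). Control targets: 625, 750 or 800 mL by weight class (Protocol Table 1). Expected mean volume: 777 mL now, 848 mL with PPN, capped at 1,000 mL (Protocol 2.1). Event rate: 0.0015 per donation; 24,000 donations (SAP 5).

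**Assumptions, because the documents give no figure.** Share of events that end the draw: 10–50%. Stopping point as a fraction of target: uniform over 0–100% or 50–100% (early), or only 90–100% (late). Event-free draws short for other causes: 1–5%, uniform over the target. Other moderate or severe events, kept in MITT and PP: 0 or 0.3%. PPN targets: normal, mean 853, SD 110, capped at 1,000 mL, which gives the stated mean of 848 mL.

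**Step 1, check of the set-up.** Passing the Appendix 2 weights through Table 1 gives a mean control target of 777 mL, the Protocol's figure. The plan gives no figure for the event-by-volume analysis itself.

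**Step 2, the specified model with no true volume effect.** Large-sample logistic fit of event on arm and collected volume; true odds ratio (OR) 1.00 per 100 mL. The worked example has 25% of events ending the draw and 5% other short draws.

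| Fitted OR per 100 mL | ITT | MITT | PP |
|---|---|---|---|
| Worked example, stops uniform 0–100% | 0.74 | 0.60 | 0.35 |
| Same, stops only at 90–100% | 1.07 | 1.01 | 0.86 |
| Full grid, early stops | 0.52–0.91 | 0.38–0.82 | 0.25–0.72 |
| Full grid, late stops | 0.86–1.13 | 0.81–1.08 | 0.75–0.95 |
| Early, with SAP 3.1.1 covariates | 0.51–0.90 | 0.38–0.79 | 0.14–0.57 |
| Late, with SAP 3.1.1 covariates | 0.82–1.17 | 0.74–1.11 | 0.61–0.91 |

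An exchangeable GEE with about four donations per donor gave 0.74–0.75, 0.60–0.62 and 0.29–0.31 for the worked example, and 1.15, 1.09 and 0.89 for late stops. Clustering therefore does not remove the pattern.

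**Step 3, other consequences.** In the worked example a null arm effect is fitted as an OR of 1.17 (ITT), 1.25 (MITT) and about 1.4 (PP). A second simulation, with slightly different target assumptions and BMI in the model, gave 0.75, 0.62 and 0.26 for volume and 1.28, 1.41 and 2.25 for arm. In it a truly harmful volume OR of 1.30 was fitted as 0.76, 0.63 and 0.29. When no event ended a draw and event draws were never short, it gave 1.25, 1.20 and 1.01: the opposite direction in ITT and MITT, and almost none in PP.

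**Step 4, the planned rate.** Rate = events / litres. At equal per-donation risk:

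- control: 0.0015 / 0.777 L = 1.93 per 1,000 L
- experimental: 0.0015 / 0.848 L = 1.77 per 1,000 L
- ratio: 777 / 848 = 0.92

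Across the simulated scenarios the ITT ratio was 0.90–0.93. Truncation by events hardly affects it: 0.0015 × 24,000 = 36 events are expected, so event draws are 0.15% of all draws.

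**Step 5, target volume as covariate.** With risk unrelated to donor size, the fitted OR for target volume was 0.99–1.01 in all sets. That result depends on the simulated independence. With no volume effect and no truncation, but baseline odds multiplied by 0.9, 0.8 or 0.7 per SD of donor plasma volume (assumed), the model with arm, BMI and target gave about 0.93, 0.83 and 0.77 per 100 mL. Collected volume gave the same when nothing was truncated.

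**The case against.** The strongest reply is that the premise is not quantified. No passage states how often an event ends a draw. SAP Appendix 2 assumes that donors stop plasmapheresis after an event, which a reader might take as proof, but it can equally mean no further donations. Protocol 2.4 places peak extracorporeal volume at the end of collection, which makes late stops plausible. This stands: a reader might infer that the analysis will show larger volumes as protective, and the documents do not support that. They support only that it can.

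Second, the sentence assigning volume analyses to MITT and PP might refer only to the collected-volume endpoint. That reading is possible, though the text more naturally covers the event-by-volume model. The ambiguity is itself a reason to state the set.

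Third, SAP 3.2 also promises relative rates by repeat-measure models and descriptive techniques, and SAP 3.5 describes collected volumes at donations with significant or severe events. The first leaves room for a rate per litre but defines no denominator. The second can reveal truncation but does not correct the coefficient. To say that the plan abandons the planned rate would go too far.

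Fourth, the remedies have limits. Events per litre favours the larger-volume arm arithmetically, and target volume is confounded by donor size: Protocol 2.1 and 2.4 themselves suggest lower risk in larger donors. Both points stand and shape the fix.

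**Conclusion.** The concern holds in a limited form. Collected volume, time and cycles can be consequences of the event, and the MITT and PP rules can strengthen the resulting association. The volume coefficient can be biased towards fewer events at larger volumes, most in PP, and the arm coefficient can be distorted with it.

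The size rests wholly on assumed truncation. With at least 10% of events ending the draw, PP stayed below 1 in every run; in ITT and MITT the bias can be absent or reversed if stops are late or rare. The specified model also does not by itself yield events per volume.

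The consequence is bounded. SAP 3.2 specifies no test of volume, nothing depends on this estimate, and the primary non-inferiority model has no volume term. A reader might infer that the primary conclusion is at risk; it is not. A reader might also infer that target volume gives an unbiased volume effect; it removes reverse causation only. The change is worth making, but it is not critical.

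**What to change.** 1. State that the event-by-volume analysis is run on ITT.
2. Define the planned relative rate as events per litre collected, by arm, with a donor-clustered confidence interval. Use either a log-link GEE with log-volume offset, independence working correlation and robust standard errors, or a donor bootstrap of total events over total litres. The bootstrap is needed if any draw collected 0 mL. Always show it beside the per-donation rate, with a note that equal per-donation risk gives a ratio of about 0.92, which is not a safety gain.
3. If a volume covariate is wanted, use the target volume set before the draw, adjust also for donor weight or calculated plasma volume, and describe the result as an association. Below the cap, the experimental target is a fixed 28.5% of calculated plasma volume, so that arm holds little separate information on volume.
4. Label models with collected volume, time or cycles in MITT and PP as descriptive, with a reverse-causation caveat.

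The cost is minor SAP wording and programming. No new data are needed: the target volume per donation is already required for the 90% rule in PP, and SAP 3.2 foresees later versions that detail the other secondary endpoints.
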